### 3.7.2 Clinical Laboratory Tests

Blood samples for chemistry, hematology, coagulation, urinalysis, and serology testing will be obtained based on schedule of procedures ([Appendix A](#)). Descriptive statistics will be provided for chemistry, hematology, coagulation parameters using the International System of Units at baseline, each scheduled post-baseline visit, the minimum post-baseline value, the maximum post-baseline value, last post-baseline value and changes from baseline for each scheduled post-baseline visit, minimum, maximum, and last post-baseline values. Both scheduled and unscheduled post-baseline values will be considered for the summaries.

A paired t-test p-value will be used to compare the baseline value with each scheduled post-baseline values. An unpaired t-test p-value will be used for the change from baseline at each scheduled post-baseline visit to compare AP-SA02 and placebo.

All clinical laboratory data will be listed by subject based on randomized subjects. Laboratory values outside the normal ranges will be flagged in the data listings.

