### 3.1.2 Definition of Baseline

Baseline is defined as the last non-missing value prior to the first dose of study drug. If a subject was randomized but not treated, the baseline value is last non-missing value on or prior to randomization date. Baseline SAB is defined as SA isolated from positive blood culture within 72 hours prior to first dose of study treatment. Blood culture results are obtained from local microbiology laboratories.

Any eligibility protocol deviation from the 72-hour blood culture timepoint (relative to randomization) will be discussed and approved for individual subject inclusion in the per protocol MITT population before database lock.

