### 3.1.3 Summary Statistics

Categorical data will generally be summarized with counts and percentages of subjects. The denominator used for the percentage calculation will be clearly defined. Continuous data will generally be summarized with descriptive statistics including n (number of non-missing values), mean, median, standard deviation, minimum, and maximum.

All data will be listed by subject based on randomized subjects.

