#### 3.7.1 Adverse Events

AEs will be captured from the date of informed consent through EOS.

All AEs will be coded to system organ class (SOC) and preferred term (PT) using MedDRA. The Investigator will grade all AEs using the National Cancer Institute Common Terminology Criteria for Adverse Events (NCI CTCAE) v5.0.

TEAEs are defined as AEs occurring after the first dose of study drug through TOC for study drug (Day 12) or through EOS for SAEs.

An overview of AEs will be provided including counts and percentages of subjects with the following:

- Any AEs
- Any TEAEs
- Any study drug related TEAEs
- Any BAT related TEAEs
- Any SAEs
- NCI CTCAE grade 3/4/5 AEs
- NCI CTCAE grade 3/4/5 TEAEs
- Any TEAEs leading to interruption of study drug

- Any TEAEs leading to withdrawal of study drug
- Any TEAEs leading to discontinuation of study
- Any AEs leading to death

Counts and percentages of subjects will also be presented by SOC and PT for each of the categories in the overview. Chi-square test p-value will be provided to compare AP-SA02 and placebo.

Listings will be presented specifically for SAEs and TEAEs leading to discontinuation of study drug based on randomized subjects.

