### 3.7.3 Vital Signs

Descriptive statistics will be provided for the vital signs measurements (e.g., systolic blood pressure, diastolic blood pressure, heart rate, SpO2 (%), respiratory rate, temperature) at baseline, each scheduled post-baseline visit, the minimum post-baseline value, the maximum post-baseline value, last post-baseline value. Average values and average changes from baseline for each scheduled post-baseline visit, minimum, maximum, and last post-baseline values will be summarized. Both scheduled and unscheduled post-baseline values will be considered for the summaries.

A paired t-test p-value will be used to compare the baseline value with each scheduled post-baseline values. An unpaired t-test p-value will be used for the change from baseline at each scheduled post-baseline visit to compare AP-SA02 and placebo.

The counts and percentages of subjects with the following potentially abnormal vital signs at any post-baseline visits will be summarized:

- Heart rate >90 beats per minute;
- Respiratory rate >20 breaths per minute;
- Systolic blood pressure  $\leq 90$  mmHg and decrease  $\geq 20$  mmHg from baseline
- Systolic blood pressure  $\geq 140$  mmHg and increase  $\geq 20$  mmHg from baseline
- Diastolic blood pressure  $\leq 50$  mmHg and decrease  $\geq 10$  mmHg from baseline
- Diastolic blood pressure  $\geq 90$  mmHg and increase  $\geq 10$  mmHg from baseline

All vital sign data will be listed by subject based on randomized subjects.

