### 3.7.4 *Electrocardiograms*

Descriptive statistics will be provided for the electrocardiogram measurements (heart rate, ventricular rate, PR interval, RR interval, QRS duration, QT interval) at any post-baseline visit, the minimum post-baseline value, the maximum post-baseline value, last post-baseline value and changes from baseline for each scheduled post-baseline visit, minimum, maximum, and last post-baseline values. Both scheduled and unscheduled post-baseline values will be considered for the summaries.

The Fridericia-corrected QT interval (QTcF) will be calculated as:

- $QTcF \text{ (msec)} = QT(\text{msec}) / (RR(\text{msec}) / 1000)^{1/3}$

Counts and percentage of subjects with QTcF intervals in the categories below will be provided at any post-baseline visits:

- Absolute QTcF interval  $\geq 450$  msec and  $\leq 480$  msec
- Absolute QTcF interval  $> 480$  msec and  $\leq 500$  msec
- Absolute QTcF interval  $> 500$  msec
- Change from baseline QTcF interval increase  $> 30$  msec
- Change from baseline QTcF interval increase  $> 60$  msec

The overall interpretation (Abnormal, Indeterminate, Normal, Not evaluable, Unknown) will be summarized via counts and percentage of subjects at each scheduled visit.

All electrocardiogram data will be listed by subject based on randomized subjects.

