### 3.7.5 *Acute Kidney Injury*

AKI will be measured at Day 1 and EOS. AKI will be defined as stage 1 or higher using modified RIFLE criteria ([Appendix D of protocol](#)) at any time within the first 7 days or new need for renal replacement therapy between Day 1 and EOS.

For Day 1 and EOS assessment per RIFLE criteria, the counts and percentage of subjects will be summarized based on categories: None, Risk (R), Injury (I), Failure (F), Loss (L), ESKD (E).

Proportion of subjects with AKI between Day 1 and EOS will be provided. Chi-square test p-value will be provided to compare AP-SA02 and placebo.

AKI will be derived based on any of below assessments:

- 1) AKI assessments with results RIFLE within first 7 days from the first dose date, or
- 2) New need for renal replacement therapy.

All AKI assessments will be listed by subject based on randomized subjects.

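### Apart from creatinine/GFR through RIFLE/AKI, SAP 3.7.2 plans no by-arm count of severe laboratory values unless they were reported as AEs, and no table that can show ALT/AST and bilirubin raised together

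*SAP*

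**What the plan says.** Laboratory evaluations are one of the three components of the Phase 1b primary safety endpoint (Protocol 7.1, SAP 2.3.1) and are also a Phase 2a endpoint (Protocol 7.2, SAP 2.3.2).

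SAP 3.7.2 summarises each chemistry, hematology and coagulation parameter at baseline and at each visit, with minimum, maximum and last post-baseline values and changes. SAP 3.1.3 defines the statistics for continuous data as "descriptive statistics including n (number of non-missing values), mean, median, standard deviation, minimum, and maximum". The arms are compared on means: "An unpaired t-test p-value will be used for the change from baseline at each scheduled post-baseline visit to compare AP-SA02 and placebo". On abnormal values the section says "Laboratory values outside the normal ranges will be flagged in the data listings".

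Other safety sections go further:
- SAP 3.7.3: "The counts and percentages of subjects with the following potentially abnormal vital signs at any post-baseline visits will be summarized".
- SAP 3.7.4: "Counts and percentage of subjects with QTcF intervals in the categories below will be provided at any post-baseline visits".
- SAP 3.7.5 counts subjects by RIFLE category at Day 1 and EOS, and compares the proportion with AKI between arms.
- SAP 3.7.1 includes "NCI CTCAE grade 3/4/5 AEs" in its overview, with a matching row for TEAEs. These rows grade reported events, not laboratory results as such.

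Under Protocol 8.1 a laboratory abnormality becomes an AE if it led to an intervention, if it led to action on study drug, or if the Investigator judged it reportable. No grade forces reporting. Protocol 4.3.2 asks for a repeat test of Grade 3 or higher laboratory abnormalities, and exclusion 15 (Protocol 4.2) sets ALT/AST limits that depend on bilirubin.

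**The concern.** In a first-in-human trial with arms of this size, the useful laboratory safety question is usually how many subjects had a severe value, not how far the mean moved. The SAP answers it for vital signs, QTcF and kidney function. For other analytes, two things are missing from the by-arm tables:

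1. A severe value that was not reported as an AE appears in no count.
2. Each analyte is tabulated separately, so ALT or AST and bilirubin raised in the same subject cannot be seen in any laboratory summary.

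A reader who wants either figure would have to build it from the listings. The stake is completeness of safety reporting. No sample size, power figure or efficacy conclusion is affected.

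**Working it through.** The plan states no figure on this point, so there is none to reproduce. The check is whether the planned statistics determine the missing counts.

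**Inputs.** Phase 2a has about 42 subjects at 2:1 (SAP 2.2.4), taken as 28 active and 14 placebo, all dosed. A Phase 1b cohort is 3 active and 1 placebo. The ULNs (ALT 40 U/L, bilirubin 20 µmol/L) and all laboratory values below are assumed for illustration.

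**1. Joint elevation.** If a subjects have raised ALT and b have raised bilirubin among n, the number with both lies between max(0, a + b − n) and min(a, b). For a = b = 3 and n = 28, that is 0 to 3.

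- ALT 150 in 3 subjects and 30 in 25: mean (450 + 750)/28 = 42.9.
- Bilirubin 50 in 3 and 10 in 25: mean (150 + 250)/28 = 14.3, SD 12.6, median 10, minimum 10, maximum 50.

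These figures are the same whether the two groups of 3 are the same people or different people. A joint count would read 3/28 (10.7%, exact 95% CI 2.3 to 28.2%) or 0/28 (0 to 12.3%). This does not depend on the assumed ULNs, because one-variable summaries cannot identify a joint count.

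**2. One analyte.** Two sets of 28 maximum ALT values, with 5 × ULN = 200:

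- Set A: 20, 24 values of 40, 210, 215, 400. Three are above 200.
- Set B: 20, 20 values of 40, 5 values of 61.13, 279.36, 400. Two are above 200.

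Both sum to 1,805 (mean 64.5), have the same SD, and have median 40, minimum 20 and maximum 400. All six planned statistics agree but the counts differ.

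A wider difference in count is possible with near-identical summaries. Compare 600, three at 190 and 24 at 30 with 600, three at 210 and 24 at 30. The counts above 200 are 1 and 4. The means are 1,890/28 = 67.5 and 1,950/28 = 69.6, and the SDs 115.8 and 118.3. Median 30, minimum 30 and maximum 600 are shared.

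The summaries are not blind to counts in general. With equal rises (assumed 400 U/L, SD 20) in 1, 2 or 3 subjects, the mean change is 14, 29 or 43 and the SD 78, 107 or 128.

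**3. The t-test.** Let k of 28 active subjects have a very large rise and nobody else change. The Welch statistic tends to √(27k/(28 − k)), which is 1.00, 1.44 and 1.80 for k = 1, 2 and 3. The SAP does not say which version of the t-test applies.

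| k of 28 (placebo 0 of 14) | Percent, exact 95% CI | Pooled p | Welch p |
|---|---|---|---|
| 1 | 3.6% (0.1 to 18.3) | 0.49 | 0.33 |
| 2 | 7.1% (0.9 to 23.5) | 0.32 | 0.16 |
| 3 | 10.7% (2.3 to 28.2) | 0.21 | 0.08 |

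The exact interval for 0/14 is 0 to 23.2%. However large the rise, these p-values get no smaller than this.

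**4. What counts can add.** The chance of at least one case is 1 − (1 − p)^n. At assumed true rates of 2%, 5% and 10% it is 43%, 76% and 95% on active, and 25%, 51% and 77% on placebo. In a 3 v 1 cohort, 1/3 has an exact interval of 0.8 to 90.6% and 0/1 of 0 to 97.5%, so only raw counts are useful there.

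**The case against.** The case against giving this much weight is strong in four respects.

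- **The residual gap is narrow.** The Investigator must review out-of-range values and judge their significance (Protocol 8.7). A value that needed intervention or action on study drug should be reported as an AE, and is then counted by arm, by SOC and PT, and by grade. What remains is a severe value that needed neither and was judged not reportable. The documents give no figure for how often that happens. This stands.
- **The maximum rows do real work.** If an arm's largest bilirubin is at or below 2 × ULN, or its largest ALT and AST are both at or below 2.5 × ULN, the joint count is zero. At an assumed 2% rate, no case among 28 has probability 0.98^28 = 57%. This stands. The rows fail only when a limit is passed, because they do not then show how many subjects passed it or whether they are the same subjects.
- **The examples are constructed.** In the 1 v 4 example a cut-off of 185 would give 4 v 4. That is fair. Set A against set B and the joint example do not rest on values placed just either side of a limit.
- **Nothing is breached.** The protocol promises summaries of laboratory data, and SAP 3.7.2 supplies them. The repeat-test rule in Protocol 4.3.2 does not oblige the SAP to tabulate grades.

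A reader might infer that severe laboratory values would go unseen, or that mean-based tables hide them. The documents do not support that: SAP 3.7.2 lists all laboratory data by subject with flags, and the AE tables should carry most clinically significant abnormalities. Nor can it be said that the final output will lack these counts, since programming specifications are a separate document (SAP 7). The SAP simply does not commit to them.

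**Conclusion.** The point holds as a minor safety-analysis gap. Outside RIFLE/AKI, a severe laboratory value not reported as an AE is in no by-arm count, and joint ALT/AST and bilirubin elevation cannot be recovered from one-analyte summaries. The white-cell criterion among the signs of SAB (SAP 3.3.4 and 3.6) does not fill the gap, because it serves baseline description and time to resolution.

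In the worked case the unseen difference is 0 v 3 of 28 subjects with joint elevation, or 1 v 4 of 28 above a single limit. How often such cases would arise is unknown. The joint-count result and the limiting t-tests need no assumed ULN; the other figures rest on the stated assumptions and on 28 and 14 dosed subjects. The stronger reading, that the safety evaluation is unreliable without these counts, is not supported. The change is worth making because it is cheap and brings laboratory data into line with vital signs and QTcF.

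**What to change.** Keep the planned summaries and listings. Add to SAP 3.7.2, by arm within phase, from central-laboratory results at scheduled and unscheduled visits:

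- **(a)** For analytes with numeric CTCAE v5.0 limits only, a shift table from baseline to worst post-baseline grade, and the count and percentage of subjects with a new or worsened Grade 3 or higher value.
- **(b)** The count of subjects with post-baseline ALT or AST >5 × ULN regardless of bilirubin, and the count with ALT or AST >2.5 × ULN and total bilirubin >2 × ULN in the same blood sample.

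The cut-offs in (b) are borrowed from exclusion 15 for consistency; 15a itself applies only when bilirubin is <2 × ULN. Exclusion 15 already bars these elevations at Screening, so baseline correction matters mainly for (a). SAP 3.1.2 says "Baseline is defined as the last non-missing value prior to the first dose of study drug", and Day 1 laboratory samples follow the second infusion (Protocol 8.7), so the scheduled baseline is Screening.

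Give exact 95% CIs for pooled arms only, raw counts for Phase 1b dose cohorts, and no p-values.

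The cost is SAP wording, some programming and a few extra tables from data already collected. Many cells will hold few or no cases.

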### 3.7.3 Vital Signs

Descriptive statistics will be provided for the vital signs measurements (e.g., systolic blood pressure, diastolic blood pressure, heart rate, SpO2 (%), respiratory rate, temperature) at baseline, each scheduled post-baseline visit, the minimum post-baseline value, the maximum post-baseline value, last post-baseline value. Average values and average changes from baseline for each scheduled post-baseline visit, minimum, maximum, and last post-baseline values will be summarized. Both scheduled and unscheduled post-baseline values will be considered for the summaries.

A paired t-test p-value will be used to compare the baseline value with each scheduled post-baseline values. An unpaired t-test p-value will be used for the change from baseline at each scheduled post-baseline visit to compare AP-SA02 and placebo.

The counts and percentages of subjects with the following potentially abnormal vital signs at any post-baseline visits will be summarized:

- Heart rate >90 beats per minute;
- Respiratory rate >20 breaths per minute;
- Systolic blood pressure  $\leq 90$  mmHg and decrease  $\geq 20$  mmHg from baseline
- Systolic blood pressure  $\geq 140$  mmHg and increase  $\geq 20$  mmHg from baseline
- Diastolic blood pressure  $\leq 50$  mmHg and decrease  $\geq 10$  mmHg from baseline
- Diastolic blood pressure  $\geq 90$  mmHg and increase  $\geq 10$  mmHg from baseline

All vital sign data will be listed by subject based on randomized subjects.

### 3.7.4 *Electrocardiograms*

Descriptive statistics will be provided for the electrocardiogram measurements (heart rate, ventricular rate, PR interval, RR interval, QRS duration, QT interval) at any post-baseline visit, the minimum post-baseline value, the maximum post-baseline value, last post-baseline value and changes from baseline for each scheduled post-baseline visit, minimum, maximum, and last post-baseline values. Both scheduled and unscheduled post-baseline values will be considered for the summaries.

The Fridericia-corrected QT interval (QTcF) will be calculated as:

- $QTcF \text{ (msec)} = QT(\text{msec}) / (RR(\text{msec}) / 1000)^{1/3}$

Counts and percentage of subjects with QTcF intervals in the categories below will be provided at any post-baseline visits:

- Absolute QTcF interval  $\geq 450$  msec and  $\leq 480$  msec
- Absolute QTcF interval  $> 480$  msec and  $\leq 500$  msec
- Absolute QTcF interval  $> 500$  msec
- Change from baseline QTcF interval increase  $> 30$  msec
- Change from baseline QTcF interval increase  $> 60$  msec

The overall interpretation (Abnormal, Indeterminate, Normal, Not evaluable, Unknown) will be summarized via counts and percentage of subjects at each scheduled visit.

All electrocardiogram data will be listed by subject based on randomized subjects.

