7.3 Efficacy Outcome Assessments

Clinical outcome will be assessed at TOC for study drug, TOC for BAT, and EOS, and will be based on the definitions in Table 2. The signs and symptoms of SAB include the following:

- Documented temperature $\geq 38.0^{\circ}\text{C}$ (100.4°F) or $\leq 36.0^{\circ}\text{C}$ (96.8°F) measured orally, $\geq 38.5^{\circ}\text{C}$ (101.3°F) or $\leq 36.5^{\circ}\text{C}$ (97.7°F) measured tympanically, or $\geq 39^{\circ}\text{C}$ (102.2°F) or $\leq 37^{\circ}\text{C}$ (98.6°F) measured rectally;
- Heart rate >90 beats per minute;
- Respiratory rate >20 breaths per minute;
- White blood cell count $\geq 12.0 \times 10^9$ cells/L or $\leq 0.4 \times 10^9$ cells/L, or $\geq 10\%$ immature neutrophils;
- Systolic blood pressure <90 mmHg; and/or
- Pain associated with focal site of infection.

Note: On Day 7, the Investigator will provide an assessment of whether additional imaging is needed for potential metastatic infection based on clinical signs/symptoms of SA infection.

Table 2. Definition of Clinical Outcome

Clinical Outcome	Definition
Improvement or response (meets all criteria)	
 • The subject is alive; • Eradication of SAB based on blood cultures obtained through Day 7; • No new metastatic foci including and after Day 7 or complications of SAB; and • Resolution of SAB-related clinical signs and symptoms that were present at baseline.
No response (meets 1 or more criteria)	
 • Death due to any cause; • Persistence of bacteremia based on blood cultures obtained through Day 7 or recurrence of SAB; • Development of new metastatic foci after Day 7 or other complications related to SA; or • Persistence, worsening, or recurrence of attributable signs and symptoms of SAB which were present at baseline.
Indeterminate	Study data not available for the evaluation of efficacy due to lost to follow-up, withdrawal of consent, or missing data.

SA = *Staphylococcus aureus*; SAB = *Staphylococcus aureus* bacteremia.

7.4 National Early Warning Score 2

Table 3 presents the NEWS2 scoring system. A NEWS2 score will be recorded once per day (and should be repeated if there is a change in clinical status) from Day 1 through Day 7 and TOC for study drug (Day 12). NEWS2 is an aggregate scoring system derived from 6 physiologic parameters:

- Respiration rate;
- Oxygen saturation;
- Systolic blood pressure;
- Pulse rate;

- Level of consciousness or new confusion; and

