8.10 Electrocardiogram

A 12-lead ECG will be conducted at Screening, post first dose on Day 1, Day 3, EOT for study drug (Day 5), TOC for study drug (Day 12), TOC for BAT, and EOS. The Investigator will evaluate ECGs for abnormal results and document the clinical significance of these, reporting as AEs or medical history where appropriate.

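### SAP 3.7.4 summarises change from baseline for uncorrected QT but gives QTcF only as threshold counts; QTcF should join the continuous summaries

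*SAP*

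**What the plan says.** SAP 3.7.4 names the ECG variables to be summarised: "Descriptive statistics will be provided for the electrocardiogram measurements (heart rate, ventricular rate, PR interval, RR interval, QRS duration, QT interval"). These receive visit values, minimum, maximum and last values, and changes from baseline. The list is closed, and QTcF is not on it.

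The same section then introduces the correction ("The Fridericia-corrected QT interval (QTcF) will be calculated as") and gives the Fridericia formula, QT divided by the cube root of RR in seconds. QTcF is reported one way: "Counts and percentage of subjects with QTcF intervals in the categories below will be provided at any post-baseline visits". The categories are three absolute bands starting at 450 msec and two change categories ("Change from baseline QTcF interval increase" above 30 and above 60 msec). No mean, median or mean change of QTcF is planned there. Protocol 8.10 does not add one, and SAP Section 6 does not mention the matter. Individual values remain available: "All electrocardiogram data will be listed by subject based on randomized subjects".

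Two other provisions fix what change from baseline means. SAP 3.1.2: "Baseline is defined as the last non-missing value prior to the first dose of study drug". Protocol 8.10: "A 12-lead ECG will be conducted at Screening, post first dose on Day 1, Day 3, EOT for study drug (Day 5"), then at TOC for study drug, TOC for BAT and EOS. The Day 1 ECG follows the first dose, so the only scheduled pre-dose ECG is the Screening one.

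**The concern.** Uncorrected QT depends on heart rate, and this protocol expects heart rate to change. "Heart rate >90 beats per minute" is one of the signs of bacteremia in Protocol 7.3 (and one of six alternative Phase 2a entry signs in Protocol 4.1). Clinical response requires the signs present at baseline to resolve. A baseline ECG taken in acute illness followed by ECGs in recovery will show QT lengthening even if repolarisation is unaffected.

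The only planned mean-change output on repolarisation therefore mixes recovery with any drug effect. The output free of most of that mixing, QTcF, is reduced to counts, which discard most of the information on a modest average shift in a trial this small. The study is first-in-human and ECGs are among its safety assessments (Protocol 8 and 9.2.2), so the mean QTcF change by arm is something readers will look for.

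**Working it through.** **Inputs from the documents.** The Fridericia formula (SAP 3.7.4). Phase 2a size of about 42 at 2:1, hence 28 AP-SA02 and 14 placebo (SAP 2.2.4). Change categories of 30 and 60 msec (SAP 3.7.4). The documents state no ECG design figure, so there is none to reproduce.

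**Assumptions.** The documents give no SD for QTcF change; 15, 20 and 25 msec are used. QTcF levels and heart rates are illustrative.

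**Step 1: heart-rate effect within an arm.** Invert the SAP formula: QT = QTcF × (60/HR)^(1/3). Hold QTcF at 420 msec and let heart rate fall to 80 bpm, where QT = 420 × (60/80)^(1/3) = 381.6 msec.

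| Baseline HR | QT at baseline | QT at 80 bpm | Apparent change |
|---|---|---|---|
| 95 | 360.4 | 381.6 | +21 |
| 100 | 354.2 | 381.6 | +27 |
| 110 | 343.2 | 381.6 | +38 |
| 120 | 333.4 | 381.6 | +48 |

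With QTcF fixed anywhere from 400 to 440 msec the range is about +20 to +51 msec. In QTcF itself the change is zero in every row.

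**Step 2: what is left against placebo.** Suppose both arms start at the same heart rate, AP-SA02 subjects end at 80 bpm, and there is no drug effect on QTcF.
- Placebo also ends at 80: difference 0.
- Placebo ends at 85: QT there is 374.0, so the false difference is 381.6 − 374.0 = 7.6 msec.
- Placebo ends at 90: QT there is 366.9, so the false difference is 381.6 − 366.9 = 14.7 msec.

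**Step 3: how well the counts stand in for the mean.** Take QTcF change at one visit as normal with mean d on AP-SA02 and 0 on placebo. The probability of exceeding 30 msec is 1 − Φ((30 − d)/SD). Exact power of a two-sided 5% chi-square test on that count is compared with noncentral-t power on the mean change, 28 versus 14. SAP 3.7.4 plans no ECG test, so power is only a yardstick.

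| Shift d | SD | Above 30 msec, AP-SA02 vs placebo | Power, count | Power, mean change |
|---|---|---|---|---|
| 15 | 15 | 16% vs 2% | 11% | 85% |
| 15 | 20 | 23% vs 7% | 21% | 61% |
| 15 | 25 | 27% vs 12% | 20% | 43% |
| 20 | 15 | 25% vs 2% | 46% | 98% |
| 20 | 20 | 31% vs 7% | 45% | 85% |
| 20 | 25 | 35% vs 12% | 37% | 66% |
| 30 | 15 | 50% vs 2% | 98% | over 99% |
| 30 | 20 | 50% vs 7% | 89% | 99% |
| 30 | 25 | 50% vs 12% | 76% | 95% |

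**Step 4: precision of the missing summary.** The 95% CI half-width for the between-arm mean difference is t(0.975, 40 df) × SD × √(1/28 + 1/14) = 2.021 × SD × 0.327, which is 9.9, 13.2 or 16.5 msec for SD 15, 20 or 25.

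**The case against.** Several points on the other side stand.

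- Safety is compared with concurrent randomised placebo, and both arms receive BAT (SAP 3.7). Equal recovery of heart rate removes the artefact from the comparison.
- Heart rate and RR are summarised beside QT in SAP 3.7.4, and heart rate is compared between arms in SAP 3.7.3. An attentive reader would see the heart-rate fall next to the QT rise. Arm means of QT and RR do not, however, give the mean change in QTcF.
- Large shifts and outliers are not hidden. The change and absolute categories, the overall interpretation and the listings all remain.
- ECG is not among the named Phase 1b primary safety summaries (Protocol 7.1) or the Phase 2a endpoints (Protocol 7.2).

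A reader might infer that a drug that works will look QT-prolonging by a definite amount. With QTcF at 400 msec and heart rate falling from 100 to 75, QT goes from 337 to 371 msec (+34). Multiplying by the sizing assumption of 80% versus 30% response gives (0.8 − 0.3) × 34 = 17 msec. The documents do not support that figure. It starts every subject at 100 bpm, while Protocol 4.1 needs only one of six signs. It also treats a composite response rate as the rate at which tachycardia resolves. If half the subjects are tachycardic it is 8.5 msec; if heart rate resolves in 60% of placebo subjects it is (0.8 − 0.6) × 34 = 6.8 msec; with both it is 3.4 msec.

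A reader might also infer that the counts would miss most real QTcF effects. Step 3 shows this for shifts of 15 to 20 msec, but not near 30 msec. Nor would the mean change reliably detect a small effect: at 10 msec its power is only 22-51%.

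**Conclusion.** The point holds as a gap in the analysis. The SAP gives a continuous summary to the heart-rate-dependent interval and withholds it from the corrected one that it already derives. Within an arm, recovery alone can move mean QT by roughly 20 to 50 msec. Between arms the distortion is zero if heart rate falls equally and about 8 or 15 msec if final heart rates differ by 5 or 10 bpm.

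For a 15 msec shift the count above 30 msec detects 11-21% against 43-85% for the mean change; for 20 msec, 37-46% against 66-98%. These figures rest on the Fridericia model, a single visit, normally distributed changes, an assumed SD of 15-25 msec and the full 28:14 allocation.

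The documents do not show that AP-SA02 will appear to prolong QT, or that large QTcF effects would go unseen. The consequence is a less interpretable safety summary that is nearly free to correct.

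**What to change.** In SAP 3.7.4, add QTcF to the list of continuously summarised variables: baseline, each scheduled visit and change from baseline, with the AP-SA02 minus placebo mean difference and its 95% CI. State that QTcF is the QT variable used for interpretation. Name baseline explicitly among the time points, as the laboratory and vital-sign sections do. Keep uncorrected QT as a supportive summary and keep the QTcF categories; nothing requires moving raw QT to listings.

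Optionally, say whether the categories are tabulated visit by visit or over all post-baseline visits together, since the wording allows either. If they are pooled, show ECGs through Day 12 (four scheduled: Days 1, 3, 5 and 12) apart from TOC for BAT and EOS. The gain is modest: with an assumed single-ECG SD of 14 msec and a shared baseline, noise alone puts about 23% of subjects above 30 msec over six ECGs and 18% over four.

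The cost is SAP wording and table shells. QTcF and its change from baseline are already derived for the categories, and no new data are needed.
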